If the SAE is not previously documented in the Investigator's Brochure or Package Insert (new occurrence) and is thought to be related to the investigational treatment, a Drug Safety and Epidemiology Department associate may urgently require further information from the investigator for Health Authority reporting. Novartis may need to issue an Investigator Notification (IN) to inform all investigators involved in any study with the same investigational treatment that this SAE has been reported. Suspected Unexpected Serious Adverse Reactions (SUSARs) will be collected and reported to the competent authorities and relevant ethics committees in accordance with Directive 2001/20/EC or as per national regulatory requirements in participating countries, except for SUSARs that are also efficacy endpoints and exempted from such expedited reporting as detailed below.

Study-specific expediting rules for SUSARs that are also efficacy endpoints

In studies such as this one, where the efficacy endpoints potentially meet the requirements for SUSAR reporting, the integrity of the study may be compromised if the endpoints are systematically expedited to competent authorities/relevant ECs and investigators. In such cases, regulations allow an exemption from SUSAR expediting aimed at ensuring the validity of an outcome study (European Commission: Communication from the Commission CT-3 (2011/C 172/01); FDA Guidance 2012). Therefore, the rules for expediting SUSARs during the 14-day SAE collection period will be applied as follows.

1. Endpoint events that will not be expedited

A SUSAR will not be expedited, if the event is considered consistent with one of the efficacy endpoints:

- From randomization through Day 5: renal deterioration (defined as ≥ 0.3 mg/dL increase in serum creatinine)
- From randomization through Day 14: in-hospital worsening heart failure (WHF) requiring rescue therapy (see endpoint definition in Section 2), or all cause death, or readmission for heart failure (HF)
- Definitions:

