 - In-hospital WHF includes worsening signs and/or symptoms of heart failure that require an intensification of intravenous therapy for heart failure or assisted (invasive or non-invasive) ventilation, renal or circulatory support. Such treatment can include the institution or up-titration of IV furosemide, IV nitrates or any other IV medication for heart failure, or institution of mechanical support such as assisted (invasive or non-invasive) ventilation, ultrafiltration, hemodialysis, intra-aortic balloon pump or ventricular assist device, etc.
 - HF signs and symptoms include, but are not limited to, dyspnea on exertion or at rest, orthopnea, rales, jugular venous pulse (JVP) and peripheral edema.

In addition, Novartis will not expedite a report to competent authorities/relevant ECs and will not issue an IN.

If specifically requested by a local Health Authority, pre-specified endpoints (see above) that also meet the criteria for SUSARs will be expedited to this Health Authority. Investigator Notifications will not be issued for these events.

2. Endpoint events that will be expedited

There is a subset of SAEs, which will require expedited reporting to competent authorities/relevant ECs and investigators, if these meet SUSAR and/or endpoint criteria and are indicative of one of the following events:

- Fatal events, which are often associated with drug toxicity and which include SAEs indicative of anaphylaxis, angioedema, blood dyscrasias (including agranulocytosis, aplastic anemia, bone marrow failure, pancytopenia and bicytopenia), hepatic injury, inflammatory lung disorders (including allergic, fibrosing, necrotizing alveolitis, eosinophilic pneumonia and interstitial lung disease), rhabdomyolysis, and serious cutaneous skin reactions (including Stevens-Johnson syndrome, toxic epidermal necrolysis and erythema multiforme) torsade de pointes and prolonged QT interval.

- Efficacy endpoints, for which the investigator considers that the character and the severity of the endpoint is not consistent with the expected presentation or course of that endpoint and the investigator considers that the study drug and/or study procedures may have contributed to this abnormal presentation.

Study-specific expediting rules for SUSARs that are commonly observed in the study population

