In clinical trials evaluating treatments for high morbidity and/or high mortality disease states, SAEs that are known consequences of the underlying disease or condition under investigation, or events common in the study population, are anticipated to occur with some frequency during the course of the trial, regardless of drug exposure. While the investigator must still report all non-serious AEs and SAEs through Day 5, and through Day 14, respectively, SUSARs considered consistent with the following SAE Preferred Terms (PTs) will not be reported in an expedited timeframe to regulatory agencies, ECs or investigators during the course of the study:

abdominal pain, acute coronary syndrome, acute pulmonary edema, anaemia, angina pectoris *, anxiety, arthralgia, asthenia, azotaemia, back pain, blood creatinine *, blood pressure *, blood urea nitrogen *, bronchitis *, cardiac arrest, cardiac arrhythmias (all PTs presenting any type of arrhythmia **excluding** electrocardiogram QT interval abnormal, electrocardiogram QT prolonged, long QT syndrome, torsade de pointes), cardiac asthma, cardiac failure *, cardiac output *, cardiac pacemaker *, cardiac tamponade, cardiogenic shock, cardiorenal syndrome, cerebrovascular accident, chest pain, chronic obstructive pulmonary disease, confusional state, constipation, cor pulmonale *, cough *, creatinine renal clearance *, delirium, diarrhea, dizziness, dyspnea *, ejection fraction *, fatigue, generalized oedema, glomerular filtration rate *, gout, headache, hepatic congestion, hyperglycemia, hyperkalemia, hyperlipidemia, hypertension *, hyperuricaemia, hypoglycemia, hypokalemia, hypernatremia, hypotension *, implantable defibrillator *, influenza *, insomnia, loss of consciousness, muscle spasm, musculoskeletal pain, myocardial infarction*, nasopharyngitis, nausea, edema, edema due to cardiac disease, edema peripheral, osteoarthritis, pain in extremity, pericardial effusion, pleural effusion, pneumonia *, presyncope, pulmonary hypertension, pulmonary edema, renal failure *, renal impairment, respiratory distress *, respiratory failure *, respiratory tract infection *, stroke *, syncope, transient ischemic attack, urinary tract infection, valve *, ventricular failure *, vomiting, weight increased.

*More than one PT can contain this term.

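### Protocol section 7.2 both requires and rules out expedited reporting of an atypical efficacy endpoint, suspected to be drug-related, that is consistent with a listed common term

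*Protocol*

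**What the plan says.** Protocol section 7.2 starts from a default: SUSARs are reported to authorities and ethics committees unless they are efficacy endpoints exempted by the rules that follow. Two separately headed sets of rules then appear.

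The first concerns SUSARs that are also efficacy endpoints, within the 14-day SAE collection period.
- Rule 1 lists endpoint events that are not expedited. It opens with "From randomization through Day 5: renal deterioration" and then covers in-hospital WHF, all-cause death and readmission for heart failure through Day 14.
- Rule 2 lists endpoint events that are expedited: "There is a subset of SAEs, which will require expedited reporting to competent authorities/relevant ECs and investigators, if these meet SUSAR and/or endpoint criteria". Its second bullet covers "Efficacy endpoints, for which the investigator considers that the character and the severity of the endpoint is not consistent with the expected presentation" or course, provided that "the investigator considers that the study drug and/or study procedures may have contributed to this abnormal presentation".

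The second concerns SUSARs that are common in the study population. Those considered consistent with a list of Preferred Terms "will not be reported in an expedited timeframe to regulatory agencies, ECs or investigators during the course of the study". The list contains "cardiac failure *, cardiac output *, cardiac pacemaker" and "renal failure *, renal impairment, respiratory distress", and elsewhere pulmonary edema, cardiogenic shock, ventricular failure, blood creatinine and glomerular filtration rate. Its entry for arrhythmias leaves out "electrocardiogram QT interval abnormal, electrocardiogram QT prolonged, long QT syndrome, torsade de pointes". After the list, a local health authority may ask to receive such events, but investigators are not notified of them.

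**The concern.** Rule 2 and the list name the same three recipients and tell the sponsor to do opposite things. The list asks only whether the event is consistent with a Preferred Term. An unusual presentation, or a suspicion that the drug contributed, does not take an event off it.

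Rule 2 is the one stated route by which an endpoint with an abnormal presentation and a possible drug contribution is sent out quickly. Such events are also the easiest to attribute to the underlying disease, because they look like the condition being treated. If safety staff follow the list literally, that route is closed for events consistent with its terms. Authorities, ethics committees and investigators would then not hear of them in an expedited timeframe.

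**Working it through.** No arithmetic applies: the point turns on the scope, recipients, period and exceptions of the provisions in section 7.2.

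**Can one event meet both provisions?** It must be an efficacy endpoint, atypical in character and severity, with a suspected contribution (rule 2). It must also be a SUSAR consistent with a listed term (the list).
- *WHF.* Protocol section 7 requires every WHF endpoint to be recorded as an AE or SAE as well, and recommends wording that names worsening of heart failure. Coding to a cardiac failure term is the natural result, and that term is listed.
- *Renal deterioration.* The endpoint is defined by a serum creatinine rise of at least 0.3 mg/dL. The list contains creatinine, glomerular filtration rate, renal failure and renal impairment terms. No wording is recommended for these events, so the coding here is an inference.
- *Limit.* An endpoint attributed only to a study procedure may not be a SUSAR at all. It would then fall outside the list and raise no conflict.

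**Applying the text to cases** (all SUSARs consistent with a listed term):

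| Event | Endpoint rules | Common-term list | Result |
|---|---|---|---|
| Ordinary WHF, through Day 14 | Rule 1: not expedited | Not expedited | Agree |
| Ordinary renal deterioration, through Day 5 | Rule 1: not expedited | Not expedited | Agree |
| Atypical WHF, drug suspected, through Day 14 | Rule 2: expedited | Not expedited | Conflict |
| Atypical renal deterioration, drug suspected, through Day 5 | Rule 2: expedited | Not expedited | Conflict |
| Renal event, Days 6 to 14 | Rule 1 exemption has ended | Not expedited | No contradiction; intent not stated |
| Drug-related cardiac failure event after Day 14 | Rule 1 exemption has ended | Not expedited | No contradiction; intent not stated |

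**Does any sentence resolve rows three and four?**
- The list's only term-level exclusion is the QT and torsade group. Rule 2's first bullet names torsade de pointes and prolonged QT among its fatal events, so the list does make room for one group that rule 2 mentions. It makes none for the atypical endpoints in the second bullet.
- The local-authority sentence restores reporting only to the authority that asks. Rule 2 also requires notice to investigators, which that sentence excludes.
- The opening default mentions only exempted efficacy endpoints as its exception. It is silent on the list and on precedence.

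**The case against.** The best reply is that the two headings define two classes of SUSAR, with endpoints governed only by the first. Each set has its own local-authority sentence, one for pre-specified endpoints and one for common adverse events, which suggests two classes. The list is justified by events expected with some frequency whether or not the drug is given, whereas rule 2 concerns an abnormal presentation to which the drug may have contributed. Read so that every rule has effect, the specific rule 2 would govern atypical endpoints.

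This reading is reasonable and may be what was meant, but the text does not state it. The list is not limited to non-endpoint events, its test is consistency with a term, and its rationale also covers known consequences of the disease under study, which describes WHF.

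Other parts of the reply stand in full. Every SAE through Day 14 must reach the sponsor within 24 hours (Protocol section 7.2), and later SAEs are reported if a causal relationship is suspected. An independent DMC reviews safety data throughout (Protocol section 8.4, SAP section 5.4). A reader might infer that a safety signal would go undetected, but the documents do not support that: what is at risk is prompt external notice.

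**Conclusion.** Section 7.2 contains a real conflict, limited to efficacy endpoints that are atypical in character and severity, have a suspected drug contribution and are consistent with a listed term. The documents give no figure for how many such events to expect. The conclusion rests on two assumptions: that these endpoints code to listed terms, which is well supported for WHF and inferred for renal deterioration, and that the list reaches endpoints, which its wording allows. The primary analysis, alpha and sample size are unaffected.

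Two stronger readings are tempting but not supported. One is that nearly all WHF and renal endpoints are caught between the rules. They are not, because rule 1 and the list agree for ordinary endpoints; the number of heart failure and renal terms shows the breadth of the list, not the number of affected events. The other is that the list overrides the Day 5 and Day 14 limits of rule 1. No order of precedence is stated. Rule 1 protects study integrity over the endpoint windows, while the list rests on background frequency of disease events. Two exemptions with different grounds and periods can coexist, so later renal or heart failure events raise a question of intent rather than a contradiction.

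**What to change.** Reconcile rule 2 and the list by adding one sentence at the end of the list in Protocol section 7.2: the list does not apply to an event that meets the conditions under *2. Endpoint events that will be expedited*. Make the same change in the Safety Manual if it repeats these rules.

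As a secondary clarification, state whether the list is meant to cover endpoint-type events after rule 1's windows close (Day 5 for renal deterioration, Day 14 for WHF, death and readmission).

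The cost is one or two sentences and a few more expedited reports. Because rule 2 covers only a narrow subset, this would not become the systematic expediting of endpoints that section 7.2 seeks to avoid.

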7.3 Liver safety monitoring

Hepatotoxicity clinical safety standard guideline

Hepatic dysfunction as sequelae of HF, even with modest cardiac compromise, has long been recognized. Passive hepatic congestion due to increased central venous pressure and low hepatic perfusion, reflecting impaired hemodynamics due to decreased cardiac output and profound hypotension, are considered causative mechanisms. Subsequent atrophy of liver

cells and edema of the peripheral hepatic parenchyma both lead to hepatocellular hypoxia. PaO₂ alterations can also add to hepatic injury. These events may be both acute with cardiac decompensation and chronic with low-grade hepatic compromise resulting in fibrosis or cirrhosis (Alvarez and Mukherjee 2011; Nikolau et al 2013).

Since cardiac-induced hepatic injury can mask hepatotoxic events, it is important to clearly determine the underlying cause of elevations of liver function tests (LFTs) that may occur during the course of this study. Therefore, to ensure patient safety and enhance reliability in determining the hepatotoxic potential of an investigational drug, a standardized process for identification, monitoring and evaluation of hepatic events has to be followed.

The following two categories of abnormalities/liver events have to be considered during the course of the study:

- Liver laboratory triggers, which will require repeated assessments of the abnormal laboratory parameter
- Liver events, **which cannot be solely explained by apparent cardiac decompensation as the underlying cause (i.e., another etiology is suspected to cause or contribute to this event)** and which will require close observation, follow-up monitoring and completion of the standard base liver CRF pages

Please refer to [Table 14-1](#) in [Appendix 2](#) for complete definitions of liver laboratory triggers and liver events.

Every laboratory trigger or liver event **that cannot be solely explained by apparent cardiac decompensation as the underlying cause** and as defined in [Table 14-1](#) of Appendix 2 shall be followed up by the investigator or designated personnel at the trial site as summarized below. Detailed information is outlined in [Table 14-2](#) in Appendix 2.

For the liver laboratory trigger:

- Repeating the LFT within the next week to confirm elevation

Repeat laboratory tests should be entered on the appropriate unscheduled local laboratory CRF page.

- If the elevation is confirmed, close observation of the patient will be initiated, including consideration of treatment interruption if deemed appropriate.

For the liver events:

- Repeating the LFT to confirm elevation as appropriate
- Discontinuation of the investigational drug if appropriate
- Hospitalization of the patient if appropriate
- A causality assessment of the liver event via exclusion of alternative causes (e.g., disease, co-medications)
- An investigation of the hepatic event that needs to be followed until resolution.

These investigations can include serology tests, imaging and pathology assessments and a hepatologist's consultancy, based on investigator's discretion. All follow-up information, and the procedures performed should be recorded on the appropriate eCRF pages, including the liver event overview eCRF pages.

7.4 Pregnancy reporting

To ensure patient safety, each pregnancy occurring while the patient is on study treatment must be reported to Novartis within 24 hours of learning of its occurrence. The pregnancy shall be followed up to determine outcome, including spontaneous or voluntary termination, details of the birth, and the presence or absence of any birth defects, congenital abnormalities, or maternal and/or newborn complications.

Pregnancy should be recorded on a Clinical Trial Pregnancy Form and reported by the investigator to the local Novartis Drug Safety and Epidemiology Department. Pregnancy follow-up should be recorded on the same form and should include an assessment of the possible relationship to the investigational treatment.

Any SAE experienced during pregnancy must be reported on the SAE Report Form.

8 Data review and database management

8.1 Site monitoring

Before study initiation, at a site initiation visit or at an investigator's meeting, a Novartis representative will review the protocol and eCRFs with the investigators and their staff. During the study, the field monitor will visit the site regularly to check the completeness of patient records, the accuracy of entries on the eCRFs, the adherence to the protocol and to Good Clinical Practice, the progress of enrollment, and to ensure that study treatment is being stored, dispensed, and accounted for according to specifications. Key study personnel must be available to assist the field monitor during these visits.

The investigator must maintain source documents for each patient in the study, consisting of case and visit notes (hospital or clinic medical records) containing demographic and medical information, laboratory data, electrocardiograms, and the results of any other tests or assessments. All information on eCRFs must be traceable to these source documents in the patient's file. The investigator must also keep the original informed consent form signed by the patient (a signed copy is given to the patient).

The investigator must give the monitor access to all relevant source documents to confirm their consistency with the eCRF entries. Novartis monitoring standards require full verification for the presence of informed consent, adherence to the inclusion/exclusion criteria, documentation of SAEs, and of data that will be used for all primary variables. Additional checks of the consistency of the source data with the eCRFs are performed according to the study-specific monitoring plan. No information in source documents about the identity of the patients will be disclosed.

8.2 Data collection

Designated investigator staff will enter the data required by the protocol into the Electronic Case Report Forms using fully validated software that conforms to 21 CFR Part 11 requirements. Designated investigator site staff will not be given access to the EDC system until they have been trained. Web based software will be used: no installation procedure will be needed. Each site will be authorized by the Administrator to access into the eCRF. Each investigator site qualified personnel would be allowed to access to the eCRF by means of a

'login mask' requiring User ID and Password and it would be possible to read, modify and update only the information he/she had previously reported. All pages should report site code and patient code. On-line validation programs check for data discrepancies and, by generating appropriate error messages, allow the data to be confirmed or corrected before transfer of the data to the Contract Research Organization (CRO) working on behalf of Novartis. The Investigator must certify that the data entered into the Electronic Case Report Forms are complete and accurate. After database lock, the investigator will receive a CD-ROM with patient data for archiving at the investigational site.

8.3 Database management and quality control

The CRO working on behalf of Novartis will review the data entered into the eCRFs by investigational staff for completeness and accuracy and instruct the site personnel to make any required corrections or additions. The Data Manager of the CRO working on behalf of Novartis will perform the cleaning session reviewing the warning messages raised by on-line checks and running post-entry checks by means of validation programs. During this process, if clarifications are needed, the Data Manager will raise queries by means of data query forms through the WEB application. Designated investigator site staff is required to respond to the query and the Data Manager will make the correction to the database on the basis of the query response. The data collection and the Queries flow as well as the on-line and off-line control checks will be detailed in the Data Management Plan and Data Validation documents

Concomitant medications entered into the database will be coded using the WHO Drug Reference List, which employs the Anatomical Therapeutic Chemical classification system. Medical history/current medical conditions and adverse events will be coded using the Medical dictionary for regulatory activities (MedDRA) terminology.

Randomization codes

and data about the study drug dispensed to the patient will be tracked using an Interactive Response Technology (IRT). The system will be supplied by a vendor. The IRT database will be sent electronically to Novartis (or a designated CRO). The occurrence of any protocol deviations will be reported during the conduct of the study until database lock.

After the database has been declared to be complete and accurate, it will be locked and made available for data analysis. Any changes to the database after that time can only be made after written agreement by Novartis Development management.

